6.5. Treatment Assessments (Week 4-48)

The following evaluations are to be completed at Weeks 4, 12, 24, 36, and 48 unless otherwise specified. Participants randomized to SBR will have, after their delayed switch, an additional visit at Week 28.

All study visits are to be completed within ± 6 days of the protocol specified visit date (based on the Day 1 visit), unless otherwise specified.

Regularly scheduled evaluations will be made on all participants whether or not they continue to receive their study treatment regimen.

- HIV Symptoms Distress Module Index is to be completed by the participant at **Weeks 4, 24, 28 (SBR only) and 48**. HIV Treatment Satisfaction Change (HIV-TSQc) is to be completed at **Weeks 4 and 24 only**. VAS Adherence Questionnaire is to be completed by the participant at **Weeks 4, 12, and 24** in Treatment Group 2 only. Participant is to read questionnaire by himself/herself and write/mark answers directly onto questionnaires
- Review of AEs and changes in concomitant medications
- Complete physical examination (**Weeks 24 and 48**) (urogenital/anorectal exams will be performed at the discretion of the Investigator) or symptom-directed physical examination, as needed
- Vital signs measurement (blood pressure, pulse, respiration rate, and temperature), including weight
- Obtain blood and urine samples as described in Sections 6.9.1 and 6.9.2
- Document dispensation and accountability for FDC of B/F/TAF dispensed for Treatment Group 1 for all visits and starting at Week 24 for Treatment Group 2.
- Participants who meet the criteria for virologic failure will be managed according to the Management of Virologic Rebound Section 6.13.1 and 6.13.2

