6.7. Post-Treatment Assessments

6.7.1. Early Study Drug Discontinuation Assessments

If the participant discontinues their study regimen prior to the Week 48 visit, the participant will be asked to return to the clinic within 72 hours of stopping study treatment for the Early Study Drug Discontinuation Visit. The participant will be asked to continue attending the scheduled study visits through the Week 48 visit. Participants on Treatment 2 (SBR) who discontinue their baseline regimen due to an AE prior to Week 24 will be asked to continue attending the scheduled study visits through the Week 24 visit.

At the Early Study Drug Discontinuation Visit, any evaluations showing abnormal results indicating that there is a possible or probable causal relationship with the study treatment regimen, will be repeated weekly (or as often as deemed prudent by the Investigator) until the abnormality is resolved, returns to baseline (Day 1) value, or is otherwise explained.

The following evaluations are to be completed at the Early Study Drug Discontinuation Visit:

- Review of AEs and changes in concomitant medications
- Complete physical examination (urogenital/anorectal exams will be performed at the discretion of the Investigator)

- Vital signs measurement (blood pressure, pulse, respiration rate, and temperature), including weight
- Obtain blood and urine samples as described in Sections 6.9.1 and 6.9.2
- Document study drug accountability for FDC of B/F/TAF dispensed

6.7.2. 30-Day Follow-up Visit

Participants who complete the study through the Week 48 Visit and do not continue their participation in the study, will be required to return to the clinic 30 days after their Week 48 Visit for a 30-Day Follow-Up Visit.

Participants who prematurely discontinue study treatment and refuse to continue in the study through the Week 48 visit will be asked to return to the clinic 30 days after the completion of the Early Study Drugs Discontinuation Visit for the 30-Day Follow-up Visit.

Those participants who prematurely discontinue study treatment and continue in the study through at least one subsequent visit after the Early Study Drug Discontinuation Visit will not be required to complete the 30-Day Follow-up Visit, as long as the visit is > 30 days after last dose.

Participants who participate post Week 48 will complete a 30-Day Follow-up Visit 30 days after the last dose of B/F/TAF.

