- f Must be completed 30 days after discontinuing study drug. For the purpose of scheduling a 30-Day Follow-Up Visit, a ± 6 days window may be used. Required for participants who permanently discontinue study drug prior to Week 48 and do not continue in the study through at least one subsequent visit after the ESDD visit. Participants who participate post Week 48 will be required to return to the clinic 30 days after the completion of study drugs for the 30-Day Follow-Up Visit.
- g Early Study Drug Discontinuation visit to occur within 72 hours of last dose of study drug. Participants will be asked to continue attending the scheduled study visits through the Week 48 Visit even if the participant discontinues study drug. Participants on Treatment 2 (SBR) who discontinue their baseline regimen due to an AE prior to Week 24 will be asked to continue attending the scheduled study visits through the Week 24 visit.
- h HIV-TSQs is to be completed at Day 1. The HIV-TSQc is to be completed at Week 4 and Week 24. Participant is to read questionnaire by himself/herself and write/mark answers directly onto questionnaires.
- i VAS Adherence Questionnaire will be administered at Day 1 and at all visits up to (and including) Week 24 for participants in Treatment Group 2 (SBR) only.
- j Complete physical exam is required at Screening, Day 1, Week 24, 48, 72, and ESDD. Urogenital/anorectal exams will be performed at the discretion of the Investigator. Symptom-directed physical examination, as needed.
- k Vital signs measurements including blood pressure, pulse, respiratory rate, and temperature.
- l All female participants will have a serum test performed at Screening. Urine pregnancy test will only be done for persons of childbearing potential. Positive urine pregnancy tests will be confirmed with a serum test.

- m FSH test is required for female participants who are <54 years old and have stopped menstruating for ≥ 12 months but do not have documentation of ovarian hormonal failure.

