3.8. Analysis Windows

3.8.1. Definition of Study Day

Study Day 1/First Dose Date is defined as the day when the first dose of B/F/TAF was taken. The first dose date is the earliest nonmissing start date of B/F/TAF study drug recorded on the Study Drug Administration eCRF.

Study Days are calculated relative to Study Day 1. For events that occur on or after the Study Day 1 date, study days are calculated as (visit date minus Study Day 1 date plus 1). For events that occurred prior to Study Day 1, study days are calculated as (visit date minus Study Day 1 date).

Last Dose Date is defined as the maximum, nonmissing end date of B/F/TAF recorded on the Study Drug Administration eCRF and “Study Drug Permanently Discontinued” box checked for participants who prematurely discontinued study drug or completed study drug according to the Study Drug Completion eCRF.

For partial or missing last dose dates, please refer to the programming specifications for imputation rule details.

Last Study Date is the latest of the study drug start dates and end dates, the clinic visit dates, and the laboratory visit dates, including the 30-day follow-up visit date, for participants who prematurely discontinued study according to the Study Completion eCRF.

Baseline value is defined as the last value obtained on or prior to Study Day 1 for all assessments.

Note: for first dose date for SBR treatment group for listings, refer to the Week 48 SAP.

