4.2. Extent of Study Drug Exposure and Adherence

4.2.1. Duration of Exposure to Study Drug

Duration of exposure will be calculated for the B/F/TAF and Delayed Switch to B/F/TAF groups. Duration of exposure to study drug will be defined as (last dose date - first dose date + 1), regardless of temporary interruptions in study drug administration, and will be expressed in weeks using up to 1 decimal place (eg, 4.5 weeks).

Duration of exposure to study drug will be summarized using descriptive statistics (n, mean, SD, median, Q1, Q3, minimum, and maximum) and as the number and percentage of participants exposed for specified periods, eg, ≥ 4 weeks (28 days), ≥ 8 weeks (56 days), ≥ 12 weeks (84 days), ≥ 24 weeks (168 days), ≥ 36 weeks (252 days), ≥ 48 weeks (336 days), ≥ 60 weeks (420 days), ≥ 72 weeks (504 days).

Summaries will be provided for participants in the B/F/TAF safety analysis set. No inferential statistics will be provided.

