* Participants with positive HCVAb postbaseline must also have negative or missing HCVAb at baseline in order to be considered as having incident HIV/HCV coinfection.

“ ” means any value can be present, as it does not affect the classification

19) HBV DNA test codes: If the result of the lab test code GET1883 (HBV DNA CAP/CTM 2.0-EDTA-CL) is listed as “>170000000”, then a reflexive test code GET1884 (HBV DNA CAP/CTM 2.0Dil-EDTA-CL) should be performed and will share the same accession number as the original GET1883 test. In this instance, use the result from GET1884 instead of GET1883 when determining HBV DNA.

20) In this study, only 3rd generation LDL is collected.

21) For nonstudy drug ARV listing, ARVs which were dosed between the first dose date and the last dose date (inclusive) will be flagged (eg, ^). However, please note, if CM end date is completely missing and the medication is not marked “Ongoing” and the CRF indicates ‘Prior ARV’, the ARV will not be flagged.

22) Last Dose Date and Last Study Date

- a) Last Dose Date for participants who permanently discontinued study drug was defined in Section 3.8.1.

If last dose date is missing (eg, only year of last dose date is known or completely missing due to lost to follow-up), the latest of the B/F/TAF study drug start dates and end dates, the clinic visit dates, and the laboratory visit dates, excluding the date of 30-day follow-up visit, will be used to impute the last dose date.

If the last dose date is a partial date (ie, month and year of last dose are known), the latest of the dispensing dates of study drug bottles, study drug start dates and end dates, and the imputed last dose date [day imputed as 15] will be used as the final imputed last dose date. However, if the dispensing date’s month is after the last dose date’s month, a data query is needed.

If the participant died and the death date is complete (ie, not partial date) and before the imputed last dose date, the complete death date should be used as the imputed last dose date.

Last Study Date is the latest of the study drug start dates and end dates, the clinic visit dates, and the laboratory visit dates, including the 30-day follow-up visit date, for participants who prematurely discontinued study or who completed study according to the Study Completion eCRF. If study drug start date or end date is partially missing (ie, only year and month are known), the day will be imputed as 15 for the purpose of this analysis.

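### The SAP's rule for a missing last dose date can count off-drug follow-up as B/F/TAF exposure, because participants who stop drug are asked to keep attending visits to Week 48

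*SAP*

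**What the plan says.** SAP section 3.8.1 sets no rule of its own for incomplete dates: "For partial or missing last dose dates, please refer to the programming specifications for imputation rule details". Appendix 6, item 22, then treats two cases differently.

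- **Completely missing, or only the year known.** The trigger reads: "If last dose date is missing (eg, only year of last dose date is known or completely missing due to lost to follow-up". The imputed value is the latest of the B/F/TAF start and end dates and visit dates; in the SAP's words, "the clinic visit dates, and the laboratory visit dates, excluding the date of 30-day follow-up visit, will be used to impute the last dose date". The only upper limit is a complete death date.
- **Month and year known.** Visit dates are not used. The rule takes the latest of the bottle dispensing dates, the drug start and end dates, and day 15 of the known month. It calls for a query if a dispensing month is later than the last-dose month.

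The protocol separates stopping drug from leaving the study. Section 6.5: "Regularly scheduled evaluations will be made on all participants whether or not they continue to receive their study treatment regimen". Section 6.7.1, on those who stop before Week 48: "The participant will be asked to continue attending the scheduled study visits through the Week 48 visit". Section 6.10 asks sites to make every attempt to retain them. Under section 6.7.2, a participant who stops drug but attends a later visit "will not be required to complete the 30-Day Follow-up Visit, as long as the visit is > 30 days after last dose". The study procedures table (Protocol Appendix 2) adds: "Early Study Drug Discontinuation visit to occur within 72 hours of last dose of study drug".

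**The concern.** Using the last visit as the last dose is sound only if attending a visit implies being on drug. In this trial it does not. The rule excludes one off-drug visit, the 30-day follow-up, which is the visit that retained discontinuers usually do not have. Their other off-drug visits, with blood draws, all remain eligible.

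The year-only case has a second gap. The imputed date is not limited to the recorded year, so a participant who stopped late in one year and attended visits in the next is given a last dose in the next year, against the data on file.

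At stake is whether off-drug time, possibly on a replacement regimen (allowed with continued study participation by the notes to the virologic rebound schema in Protocol 6.13.1), is reported as B/F/TAF experience.

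**Working it through.** The plan states no figure on this point, so there is none to reproduce. The check applies the SAP's own exposure definition to its own imputation rule.

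**Inputs**
- Exposure, SAP 4.2.1: "Duration of exposure to study drug will be defined as (last dose date - first dose date + 1", in days. First dose is Study Day 1 (SAP 3.8.1), so exposure in days equals the study day of the last dose.
- Nominal days, SAP Table 3-1: Week 4 = 28, Week 12 = 84, Week 24 = 168, Week 36 = 252, Week 48 = 336.
- Assumptions: the true last dose falls at a nominal visit, its date is missing, and the last visit attended is Week 48.

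**Step 1: what the rule returns.** With no 30-day visit, the latest clinic or laboratory visit is Week 48, so the imputed last dose is day 336. Item 22 builds the Last Study Date from the same kinds of date plus the 30-day visit. For this participant the two dates therefore coincide.

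**Step 2: excess per participant, B/F/TAF group.** Excess = (336 − true last dose day) / 7 weeks; months = weeks × 7 / 30.4375.

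| Drug stopped | True exposure | Counted | Excess |
|---|---|---|---|
| Week 4 | 4 weeks | 48 weeks | (336 − 28)/7 = 44 weeks (10.1 months) |
| Week 12 | 12 weeks | 48 weeks | (336 − 84)/7 = 36 weeks (8.3 months) |
| Week 24 | 24 weeks | 48 weeks | (336 − 168)/7 = 24 weeks (5.5 months) |
| Week 36 | 36 weeks | 48 weeks | (336 − 252)/7 = 12 weeks (2.8 months) |

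**Step 3: Delayed Switch group.** B/F/TAF starts at Week 24, so follow-up to Week 48 counts as 24 weeks. Stopping at Week 28 gives 4 true weeks (excess 20); stopping at Week 36 gives 12 true weeks (excess 12).

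**Step 4: what else moves by the same amount.**
- Adverse event and laboratory windows, last dose plus 30 days (SAP 7.1.5.1, 7.2).
- Last on-treatment proteinuria, plus 1 day (SAP 7.2.5.2).
- Concomitant medications up to last dose (SAP 7.4.2) and nonstudy ARV flags (Appendix 6, items 14 and 21): a replacement regimen would be flagged as taken alongside B/F/TAF.
- Incident HBV or HCV coinfection (SAP 8.1, 8.2): a Week 48 serology result falls on the imputed last dose date and so counts as on drug.
- Any on-treatment HIV-1 RNA output, plus 1 day (SAP Appendix 2).

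**Step 5: effect on a group summary.** The documents do not say how many participants lack a last dose date. Taking the planned 320 and assuming m affected, the shift in mean exposure is m × excess / 320:
- at 44 weeks each: m = 1, 0.14 weeks; m = 3, 0.41; m = 10, 1.4;
- at 12 weeks each: m = 1, 0.04 weeks; m = 3, 0.11; m = 10, 0.4.

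**The case against.** The strongest reply is that the case needs an unlikely combination: a participant who stops drug, keeps attending, and never supplies even a month and year. The discontinuation visit with drug accountability, the required source record of drug start, end, dispensing and return dates (Protocol 9.1.5) and data queries (9.1.6) all work against it. Attendance after stopping is requested, not assured. This stands, and it is why the number affected is likely to be very small.

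The SAP's example is loss to follow-up, and for someone lost while on drug the last visit is a reasonable proxy. This also stands; the change below keeps that use.

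For adverse events, full collection stops 30 days after the last dose (Protocol 7.3.1), with only SAEs collected beyond that (7.3.2). The summaries are participant counts, so a longer window can add events but cannot dilute a rate. That limits the adverse event effect. It does not cover laboratory tests, which are drawn at every scheduled visit and summarised by visit as change from baseline, nor exposure itself.

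Three stronger readings are tempting but not supported:
- *That the primary or key secondary result is affected.* SAP 6.1.1 and 6.2.1 say those analyses were done earlier and are not repeated. The Week 48 SAP is not among the documents, so its imputation rule is unknown.
- *That adherence is distorted.* SAP 4.2.2 ends each dispensing period at the earliest of bottle return, discontinuation and next dispensing, and drops periods with unreturned bottles. A late last dose date has little room to act.
- *That a year-only date shows the participant was still in contact.* The SAP does not say so, and the point does not depend on it.

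**Conclusion.** The rule as written gives a wrong last dose date whenever it meets a participant who stopped B/F/TAF, went on attending visits, and has no date or only a year. In the B/F/TAF group the error is 12 to 44 weeks if visits run to Week 48 and drug stopped between Weeks 4 and 36. In the Delayed Switch group it is 12 to 20 weeks for stops at Weeks 36 and 28. A year-only date may also contradict the recorded year.

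The consequence is confined to descriptive exposure, safety and on-treatment outputs of the final analysis. Group-level impact is small unless many dates are missing; zero to a few affected is an assumption, since no count is given. Confidence is high on the gap in the rule and low on whether any participant falls into it.

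**What to change.** Amend item 22 for completely missing and year-only dates:

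1. For participants recorded as having discontinued drug, exclude visits after the Early Study Drug Discontinuation visit. With that visit held within 72 hours of the last dose, the error falls to about 3 days.
2. If there was no such visit and the participant is recorded as off drug but still in the study, use the latest study drug start, end or dispensing date. This may err early: scheduled visits are up to 12 weeks apart, so a last dispensing date could precede the last dose by about that much.
3. Keep the last visit as the proxy for participants lost to follow-up while on drug.
4. Where only the year is known, cap the imputed date at the end of that year.

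The anchor should be the discontinuation visit and the drug records, because the documents define no separate date for the decision to stop. The cost is about one sentence of programming specification and no new data collection. If the SAP is already final, its section 1 requires the change to be documented in the clinical study report. A count of last dose dates imputed under this item would show whether the point mattered.
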